5.2 Dose Delay and Dose Reduction

If multiple toxicities occur, dose-modification decisions should be based on the most severe toxicity.

The dose levels and the general approach to BAL101553 dose modification on this trial are shown below. Adverse events should be treated with the appropriate maximum supportive care, and dose reductions should be clearly documented on the case report form.

Dose reductions are required for any DLT (as defined in Section 5.1). Dosing will stop until the DLT has resolved to \leq grade 1 [or tolerable grade 2 for non-hematologic toxicity] or \leq baseline. The maximum length of time that BAL101553 can be held is 7 days. After resolution, the dose of BAL101553 will be reduced by 1 dose level as stipulated below, with a maximum of 2 dose reductions. Patients who require more than 2 dose reductions will be discontinued from the study. A patient must be discontinued from the study if, after treatment is resumed at a lower dose, the same toxicity recurs with the same or worse severity. If there are any questions, the ABTC Central Office and the Study Chair should be contacted.

Table 6 BAL101553 Dose Reduction Schedule

Dose Level	BAL101553
5	15* mg daily \times 6 weeks
4	12 mg daily \times 6 weeks
3	8 mg daily \times 6 weeks
2	6 mg daily \times 6 weeks
1 (starting dose)	4 mg daily \times 6 weeks
-1	2 mg daily \times 6 weeks

* Dose reduction levels: 10 mg, 5 mg.

If the dose must be reduced below dose level -1, the patient will be taken off treatment.

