5.0 DOSE MODIFICATION FOR TOXICITY

5.1 Dose Limiting Toxicity

A DLT is defined as a clinically-significant AE or abnormal laboratory value assessed as unrelated to disease progression, intercurrent illness, or concomitant medications and meets any of the criteria below. Any DLT must be a toxicity considered at least possibly related to BAL101553 or the combination of BAL101553 and radiation.

Treatment-related DLTs are defined below. Dose limiting toxicities must have an attribution of possible, probable, or definite to BAL101553 or the combination of BAL101553 and radiation. For patients experiencing a DLT, BAL101553 will be interrupted. If the patient recovers (\leq grade 1 [or tolerable grade 2 for non-hematologic toxicity] or \leq baseline), a BAL101553 dose reduction (1 dose level reduction) is required for subsequent doses. Skipped BAL101553 doses will not be made up. If there is any question or clarification required concerning a potential DLT, the treating site should contact the ABTC Central Office to determine patient's DLT status. The ABTC Central Office, with the Study Chair, will make the final decision.

➤ **Hematological toxicities** will be considered dose limiting if any of the following occur and complete blood counts and differentials were obtained according to the mandated schedule (CBC, differential, and platelets drawn twice a week until the ANC \geq 1500/mm³ and platelets \geq 100,000/mm³):

- ANC of $<$ 500/mm³.
- Platelets $<$ 25,000/mm³.
- Febrile neutropenia
- Any hematological toxicity that prevents administration of \geq 80% of the planned BAL101553 dose

Grade 3 or 4 lymphopenia will not be considered a DLT.

➤ **Central nervous system toxicities**

- \geq **Grade 2** central nervous system (CNS) ischemia will be considered a DLT
- \geq **Grade 2** neurological toxicities that interfere with activities of daily living and do not resolve spontaneously or with steroids, anticonvulsants, or electrolyte correction within 2 weeks will be considered a DLT
- Symptomatic CNS hemorrhage of any grade will be considered a DLT.

➤ **Grade 3 and 4 non-hematological, non-CNS toxicities** will be considered dose limiting with the following exceptions:

- Grade 3 nausea, vomiting, or diarrhea without sufficient prophylaxis with a duration $<$ 3 days;
- Alopecia;
- Grade 3 fatigue;
- Grade 3 hyperglycemia that is reversible and without clinical symptoms;

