- Grade 3 electrolyte disturbances that are asymptomatic and reversible within 3 days, and do not re-occur upon continuing or re-initiation at the same dose;
- Grade 3 or 4 hypophosphatemia, unless considered clinically relevant;
- Grade 3 or 4 elevations in alkaline phosphatase;
- Grade 3 hypertension that resolved to \leq Grade 2 hypertension within 1 week either spontaneously or upon implementation of antihypertensive therapy

ABTC # 1601

NCI # ABTC-1601

PI: [name]

- A subject's first episode of deep venous thrombosis (DVT) or pulmonary embolism will not require dose modification.
- **Any adverse event that leads to missing > 6 doses of BAL101553** will be considered dose limiting.
- **Any recording of SBP > 220 mmHg or DBP > 110 mmHg or any Grade 4 hypertension** will be considered dose limiting.

ANY DLT (AS DEFINED ABOVE) CAUSING DELAY IN TREATMENT OF OVER 7 DAYS WITHOUT RECOVERY TO A \leq GRADE 1 OR BASELINE STATUS WOULD RESULT IN TAKING THE PATIENT OFF TREATMENT.

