5.2.1 Adverse Events Requiring Permanent Discontinuation of Study Drug

Patients meeting any of the following criteria will be required to permanently discontinue study drug and will be withdrawn from the study:

- Grade 4 anemia
- \geq Grade 3 serum creatinine (S-Cr $>$ 3.0 \times ULN)
- Grade 4 total bilirubin (TB $>$ 10 \times ULN)

- Grade 4 diarrhea
- Recurrent QTcF > 500 ms or > 60 ms change vs baseline
- Grade 4 hypertension
- Grade 4 neurological events that do not respond within two weeks to steroids, anticonvulsants, or electrolyte correction
- Any DLT causing a delay in treatment of over 7 days without recovery to \leq Grade 1 or baseline status. This includes \geq Grade 3 electrolyte disturbances (except for hypophosphatemia if not clinically relevant) that are symptomatic or not reversible within 3 days, or that re-occur upon continuing or re-initiation at the same dose (see Section [5.1](#)).
- Any non-treatment-related Grade 3 or Grade 4 hematologic or non-hematologic adverse event which requires a delay of treatment and which is not resolved (\leq Grade 1 or \leq baseline) within 8 days (see Section [5.3](#)).

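### The restart rule in Protocol 5.1 and 5.2 accepts a tolerable grade 2 event with no exception for CNS ischemia or symptomatic CNS hemorrhage, so a Grade 2 event of either kind can literally meet it without falling in grade

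*Protocol*

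**What the plan says.** Protocol 5.1 sets two CNS triggers below the Grade 3 level used for most other non-hematologic toxicities. From Grade 2 upward, "central nervous system (CNS) ischemia will be considered a DLT". For bleeding, "Symptomatic CNS hemorrhage of any grade will be considered a DLT". A third CNS trigger, for neurological toxicity that persists for two weeks, is outside this point.

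The consequence is the same for every DLT: "For patients experiencing a DLT, BAL101553 will be interrupted". Sections 5.1 and 5.2 then allow the drug to resume one level lower when the event is at grade 1 or lower, at or below baseline, "or tolerable grade 2 for non-hematologic toxicity". Neither section makes an exception for CNS events.

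Three provisions limit this:

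- Section 5.2 caps the interruption: "The maximum length of time that BAL101553 can be held is 7 days".
- Section 5.2 stops treatment if, after restart at the lower dose, "the same toxicity recurs with the same or worse severity".
- Section 5.1 takes a patient off treatment for a DLT "CAUSING DELAY IN TREATMENT OF OVER 7 DAYS WITHOUT RECOVERY TO A" grade of 1 or lower, or baseline. Section 5.2.1 ("Any DLT causing a delay in treatment of over 7 days without recovery to" that standard) and Section 10.1 item 7 repeat the rule.

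Section 5.2.2 sends a DLT found through a fall in the MMSE score back to the procedures of 5.2.

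**The concern.** A restart threshold is meant to show that the patient has improved before being exposed again. That works when the threshold lies below the trigger. A grade-triggered DLT outside the CNS starts at Grade 3, so restarting at grade 2 requires a fall of at least one grade. For the two CNS events the trigger was lowered and the restart threshold was not. The events given the most sensitive trigger therefore have the weakest recovery test.

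The stake is the safety of the individual patient. A DLT is by definition at least possibly related to the drug or to its combination with radiation. A patient whose CNS ischemia or symptomatic hemorrhage is unchanged could be given the drug again while cranial radiation continues. The stop rule for recurrence does not plainly help, because an event that never cleared has not clearly recurred.

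**Working it through.** The check is mainly a comparison of texts.

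**Step 1: is a CNS event non-hematologic for this rule?** Yes, on the protocol's own usage. Where 5.1 wants CNS events left out of a non-hematologic class, in its Grade 3 and 4 DLT criterion, it says so explicitly. The restart allowance carries no such qualifier.

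**Step 2: compare grade at declaration with restart grade** (both from 5.1; restart grade repeated in 5.2).

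| Event | Grade at declaration | Highest restart grade | Fall in grade required |
|---|---|---|---|
| CNS ischemia | 2 | tolerable 2 | 0 |
| Symptomatic CNS hemorrhage | 2 | tolerable 2 | 0 |
| Either event | 3 | tolerable 2 | 1 |
| Either event | 4 | tolerable 2 | 2 |
| Non-CNS, non-hematologic, grade-triggered | 3 | tolerable 2 | 1 |

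**Step 3: does another rule set a stricter restart grade within 7 days?**

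- The grade-1-or-baseline rules in 5.1, 5.2.1 and 10.1 item 7 need a delay of more than 7 days. A patient restarted by day 7 does not reach them.
- The only neurological item in 5.2.1 is a Grade 4 event that does not respond within two weeks.
- Section 5.2.2 returns to 5.2.
- Section 10.1 item 1 stops treatment for neurologic deterioration, but under the progression criterion. A DLT must be assessed as unrelated to progression.
- Central Office contact (5.1, 5.2), safety review before weekly dispensing (4.4.2), investigator discontinuation (10.0), and removal for the patient's health or unacceptable toxicity (10.1 items 3 and 6) are discretionary or set no restart grade.

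None does.

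**Step 4: compare with the protocol's treatment of unrelated events.** Section 5.3 covers Grade 3 and 4 events not related to treatment. If one requires a delay, it must reach grade 1 or lower, or baseline, with no grade 2 allowance. An unrelated Grade 3 CNS event that delays treatment must therefore recover further than a drug-related Grade 3 CNS ischemia.

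**Step 5: doses at stake for one patient.** The planned course is 6 weeks × 7 doses = 42. Assume the dose on declaration day *d* is taken, a full 7-day hold follows, and the event stays unchanged. Doses left = 42 − *d* − 7. The days are assumptions.

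- *d* = 14: 42 − 14 − 7 = 21
- *d* = 21: 42 − 21 − 7 = 14
- *d* = 28: 42 − 28 − 7 = 7

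Remaining mg as a share of planned mg (assigned dose × 42), with reductions from Table 6:

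| Reduction | Planned mg | *d* = 14 | *d* = 21 | *d* = 28 |
|---|---|---|---|---|
| 15 to 10 mg | 630 | 210 (33.3%) | 140 (22.2%) | 70 (11.1%) |
| 12 to 8 mg | 504 | 168 (33.3%) | 112 (22.2%) | 56 (11.1%) |
| 8 to 6 mg | 336 | 126 (37.5%) | 84 (25.0%) | 42 (12.5%) |
| 6 to 4 mg | 252 | 84 (33.3%) | 56 (22.2%) | 28 (11.1%) |
| 4 to 2 mg | 168 | 42 (25.0%) | 28 (16.7%) | 14 (8.3%) |

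The literal reading does not require the full 7 days; each day cut from the hold adds one dose. Under the proposed text the figure is 0, which follows directly from assuming no improvement. The percentages describe the length of course remaining, not a risk.

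**The case against.** The strongest reply is textual. Section 5.1 speaks of a patient who recovers. Section 5.2 stops dosing until the DLT has resolved to the listed level and starts the lower dose after resolution. In ordinary usage an unchanged event has done neither. This stands in part: the no-improvement reading is literal but not the only one. It does not settle the matter, because both sections define recovery by the grade list and add no requirement for a fall.

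A second reply is that safeguards exist: one level less drug, a judgement of tolerability, weekly safety review, and access to the Central Office and Study Chair. These are real and make a careless restart less likely. None sets a restart grade, and tolerable is not defined.

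A third is that a sensitive DLT trigger serves dose escalation and need not dictate the individual restart rule. That is fair as a matter of design. But the protocol already applies a grade-1-or-baseline standard in 5.3 and after 7 days, and sets event-specific restart thresholds for blood pressure in 4.6.2. A specific threshold here would be in keeping with it.

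A reader might infer more than the documents support:

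- *That a Grade 1 symptomatic hemorrhage can restart with its symptoms continuing.* This is less secure. The DLT is itself defined by symptoms, and the CTCAE grades for the term, which would show whether a symptomatic bleed can be Grade 1, are not in the documents.
- *That any CNS DLT can restart without recovery.* Grade 3 and 4 ischemia or hemorrhage must fall to grade 2, and the persistent neurological DLT is not part of this point.
- *That the MTD is affected.* A patient with a DLT counts as evaluable after one dose (Protocol 4.2.2), whatever happens at restart.

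**Conclusion.** The point holds as a gap in wording, confined to Grade 2 CNS ischemia and Grade 2 symptomatic CNS hemorrhage within the 7-day hold. For these, the stated restart threshold can be met with no fall in grade. The conclusion rests on counting CNS events as non-hematologic and on reading recovery as the grade list that defines it.

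Frequency is unknown and probably very low. The Protocol reports no CNS ischemia or hemorrhage with oral dosing, and Section 2.2 describes daily oral dosing as free of vascular toxicity. The SAP (2.4.2) already counts 26 patients in the study, against 30 in the planned enrollment table (Protocol 3.1), so few further patients may be affected. The wording would also matter if carried into the efficacy trials foreseen in Protocol 2.3.

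Reporting is not lost: the event stays in the DLT listing (SAP 5.4.1), the listing of interruptions and reductions (5.4.2) and the summaries of adverse events leading to dose modification (5.4.3). The trial's conclusions do not depend on this point. It is a cheap improvement to patient safety.

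**What to change.** In Protocol 5.1 and 5.2, insert after the sentence containing the grade 2 allowance:

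> The grade 2 allowance does not apply to CNS ischemia or symptomatic CNS hemorrhage. BAL101553 may resume at the reduced level only if the event reaches grade 1 or lower, or baseline, and for hemorrhage its symptoms have resolved, within the 7-day maximum hold; otherwise the patient goes off treatment.

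Leave the rule for other neurological DLTs as it is. Section 5.2.2 needs no edit because it refers to 5.2.

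The cost is one short insertion in two sections of an amendment, with no new data, visits or patients. A few patients with stable Grade 2 ischemia or persistent symptomatic hemorrhage would lose their remaining reduced-dose treatment.

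The text has a limit: a Grade 3 or 4 event that falls to grade 1 within 7 days (with symptoms cleared, for hemorrhage) could still be followed by a restart. Adding both events to the permanent-discontinuation list in 5.2.1 would close that too, but it is a stricter clinical choice for the sponsor.

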5.2.1 Adverse Events Requiring Permanent Discontinuation of Study Drug

Patients meeting any of the following criteria will be required to permanently discontinue study drug and will be withdrawn from the study:

- Grade 4 anemia
- \geq Grade 3 serum creatinine (S-Cr $>$ 3.0 \times ULN)
- Grade 4 total bilirubin (TB $>$ 10 \times ULN)

- Grade 4 diarrhea
- Recurrent QTcF > 500 ms or > 60 ms change vs baseline
- Grade 4 hypertension
- Grade 4 neurological events that do not respond within two weeks to steroids, anticonvulsants, or electrolyte correction
- Any DLT causing a delay in treatment of over 7 days without recovery to \leq Grade 1 or baseline status. This includes \geq Grade 3 electrolyte disturbances (except for hypophosphatemia if not clinically relevant) that are symptomatic or not reversible within 3 days, or that re-occur upon continuing or re-initiation at the same dose (see Section [5.1](#)).
- Any non-treatment-related Grade 3 or Grade 4 hematologic or non-hematologic adverse event which requires a delay of treatment and which is not resolved (\leq Grade 1 or \leq baseline) within 8 days (see Section [5.3](#)).

5.2.2 Management of Decline in Mini-Mental State Examination Score

MMSE® Score ²¹	Management
Score \geq 26 OR Decline from baseline \leq 3	No actions
Score $<$ 26 AND Decline from baseline $>$ 3	Perform Neuro Exam within 1 calendar day. Withhold dose and study-drug dispensing until Neuro Exam is performed. If Neuro Exam indicates a DLT (see Section 5.1), withhold dosing and dispensing of study drug until resolution of DLT and follow procedures in Section 5.2 . Otherwise, continue patient dosing and drug dispensation and follow general study procedures. A scheduled MMSE® can be replaced by a Neuro Exam.

5.3 Major Events

Major events are non-treatment-related grade 3 or 4 hematologic and non-hematologic adverse events. Treatment should be delayed for major events if BAL101553 may further complicate the non-treatment-related event. If a major event requires a delay of treatment, treatment must be delayed until the event is resolved (\leq grade 1 or \leq baseline). If the event is not resolved in \leq 8 days, the patient will be removed from treatment. The ABTC Central Office should be consulted if you are not clear on whether to continue or delay treatment.

5.4 Use of Hematologic Growth Factors

No growth factors (G-CSF or GM-CSF) are to be used prophylactically in this protocol. Clinicians caring for patients on this protocol are permitted to use these growth factors to

ABTC # 1601

NCI # ABTC-1601

PI: [name]

provide optimal care for patients with severe neutropenia in accordance with the ASCO guidelines, (JCO, 12, 1994: pp2471-2508). If these growth factors are used in the acute setting of neutropenia and infection (documented or suspected), they will not be utilized prophylactically in subsequent cycles and they will not subsequently be used *in lieu* of dose reduction of BAL101553.

5.5 Toxicity Criteria

All toxicities will be described and graded according to the NCI CTCAE version 4.0 until March 31, 2018; CTCAE version 5.0 will be utilized beginning April 1, 2018. All appropriate treatment areas should have access to a copy of the CTCAE version 5.0. A copy of the CTCAE version 5.0 can be downloaded from the CTEP web site (http://ctep.cancer.gov/protocolDevelopment/electronic_applications/ctc.htm). See also Section [9.2.1](#), Recording of Adverse Events.

6.0 PHARMACEUTICAL INFORMATION

BAL101553 (NSC# 789724)

BAL101553 is a water-soluble, lysine pro-drug of the synthetic small molecule BAL27862 (a furazano-benzimidazole derivative).

Chemical Name

(2S)-2,6-diamino-N-{4-[2-(2-{4-[(2-cyanoethyl)amino]-furazan-3-yl}-1*H*-benzimidazol-1-yl)acetyl]phenyl}hexanamide dihydrochloride.

Molecular Formula

C₂₆H₂₉N₉O₃ · 2HCl

Molecular Mass

588.49 g/mol

How Supplied

BAL101553 for oral administration is presented as hard capsules, each containing 1 mg or 5 mg study drug. The capsules also contain mannitol and magnesium stearate as excipients. The white/opaque capsule shell is made of HPMC.

Storage

BAL101553 1 mg capsules should be stored at temperatures between 2-8 °C.

BAL101553 5 mg capsules should be stored at temperatures between 2-25 °C.

Stability

Stability studies are ongoing, please refer to study medication label for expiration date.

Route of Administration

Oral administration. Patients must fast for a minimum of 4 hours prior to, and 1 hour after, dosing. Capsules must be taken with (at least) 250 mL of water. No other intake of food is permitted for 1 hour after taking the dose.

Known Potential Drug Interactions

ABTC # 1601

NCI # ABTC-1601

PI: [name]

Drugs that are metabolized by CYP2C9, CYP2C19, and CYP3A4

Contraindications

Patients receiving coumarin anticoagulants, phenytoin

6.1 Potential Risks

Based on the safety experience from 73 patients administered BAL101553 as 2-hour IV infusions at dose levels from 15–80 mg/m² in the Phase I and Phase IIa portions of study CDI-CS-001, dose-related patterns were reported for systemic adverse drug reactions (ADRs) of nausea/vomiting, transient arterial hypertension, reversible or partially reversible peripheral sensory neuropathy, reversible gait disturbance, myocardial injury and pain at the tumor site.

Dose-related blood pressure (BP) increases > 170 mmHg (systolic) were observed at dose levels ≥ 45 mg/m², consistent with the vascular-disrupting effect observed in animal models. The maximum BP elevations occurred ~1 hour after conclusion of the BAL101553 infusion, coinciding with the T_{max} of the active drug BAL27862 and were generally resolved within 24 hours following the IV dose.

At dose levels of 60 mg/m² and 80 mg/m², some patients presented with reproducible transient grade 2–3 abdominal pain, possibly reflecting tumor pain, which occurred during dosing and disappeared within a few hours of the end of study-drug administration.

Additional systemic side effects considered to be characteristic for BAL101553, but which did not show a clear dose relationship, included anorexia, diarrhea, fatigue and pyrexia.

Based on the safety experience from 35 patients with solid tumors or glioblastoma / high-grade glioma treated with daily-oral BAL101553 in study CDI-CS-002, clinically-relevant drug-related side effects were reversible hallucinations (Grade 2) and reversible hyponatremia (Grade 3 or Grade 4) at a dose level of ≥ 20 mg per day.

Dose levels of 8 mg per day (7 patients, including 4 patients in the GBM arm) and 15 mg or 16 mg per day (7 patients with solid tumors, 3 patients in the GBM arm) were shown to be well tolerated. Drug-related side effects at dose levels up to 16 mg per day included Grade 1/Grade 2 anemia, anorexia, arthralgia, constipation, diarrhea, fatigue, lethargy, hepatic enzyme elevations, hypokalemia, hyponatremia, nausea, nose bleed, oral candidiasis, oral mucosa dryness, paresthesia, pruritus, rash, rhinorrhea, seizure, stomatitis, xeroderma, and xerostomia; and Grade 3 hypertension (at 8 mg/day in a solid tumor patient). One solid tumor patient at 16 mg/day developed a systolic blood pressure elevation >160 mmHg which was not drug-related; however, this patient had variable pre-dose blood pressure levels and there was no clear impact on the overall blood pressure profile in this patient or in other patients treated at doses between 2 mg per day and 16 mg per day. There was also no impact on blood pressure at the maximum administered dose of 30 mg per day.

Two solid tumor patients developed a symptomatic Grade 4 hyponatremia at a daily oral dose of 20 mg per day of BAL101553, one with associated symptoms of insomnia,

ABTC # 1601

NCI # ABTC-1601

PI: [name]

dysarthria and impairment of concentration, and one with insomnia and hallucinations. One GBM patient developed Grade 2 depression and fatigue at a daily oral dose of 20 mg.

One GBM patient at a daily oral dose of 8 mg combined with radiotherapy developed Grade 2 fever and Grade 3 encephalopathy.

6.2 Agent Ordering

The Investigator, or those named as sub-investigators on the Statement of Investigator Form 1572, agree to supply study drugs only to those subjects enrolled in the study. The Investigator or designee will keep a current and accurate inventory of all clinical drug supplies provided by Basilea. The study site will maintain a dispensing log.

Once a site has submitted all required regulatory documents to ABTC and Basilea (Form 1572, curriculum vitae, licenses, IRB approval of protocol and consent), an initial supply of drug can be ordered. An ABTC drug order form, which can be found on the ABTC website (ABTConsortium.org), should be emailed to the ABTC Central Office to initiate sending of the drug. The ABTC Central Office will forward the drug order form to Basilea. Please allow 7 days from the receipt of the drug order form at Basilea for drug shipment.

